2.2. Background and Significance

Burden of injurious falls in the NH: The incidence of falls in U.S. NHs is extraordinary: 150 falls/100 bed years.¹ Consequently, falls are the leading cause of hospitalization and ED visits among NH residents.² Five to eleven percent of falls in the NH result in major injury, defined as a fracture, joint dislocation, laceration requiring sutures, or serious hemorrhage.^{1,3} Approximately one-half of injurious falls are fractures.³

Injurious falls are costly: the annual direct cost of managing hip fractures alone in U.S. NH residents exceeds \$665 million.⁴ For a single, average sized NH, the annual direct cost of injurious falls may equal \$284,000.⁵ In addition, injurious falls lead to pain⁶, functional decline,^{7,8} diminished quality of life,⁸ and frequent litigation. CMS has determined that the proportion of NH residents experiencing an injurious fall is an important quality metric,⁹ yet no standardized approach to prevent injury exists.

Efficiently target the intervention: A practical approach to preventing injury in the resource-constrained NH environment requires identification of residents at greatest risk for targeted interventions. Previously, our group published a model that estimates the two-year risk of hip fracture in NH residents: Fracture Risk Assessment in Long term care (FRAiL).¹⁰ This model is derived entirely from data collected for the validated¹¹⁻¹⁶ and routinely collected in all nursing homes through the Minimum Data Set (MDS). The model identified a unique pattern of risk factors for hip fracture not seen in community dwellers: the strongest predictors of fracture were related to falls, rather than bone mineral density (e.g., falls history, wandering). In the derivation sample, the concordance index (C-index) was 0.71 in women and 0.69 in men. We have validated the model to predict the two-year incidence of non-vertebral fracture and hospitalized injurious falls, and model performance is similar (C-index for non-vertebral fracture=0.66; for hospitalized injurious falls=0.65).

Medication management prevents injurious falls: In order to prevent injurious falls it is necessary to 1) remove modifiable risk factors for falls, and 2) manage osteoporosis such that a fracture is less likely to occur in the setting of a fall. Medications are one of the most common and modifiable risk factors for falls and osteoporosis in the NH.

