Safety	Behaviors	MDS	<10% increase	
	Functional Decline			
	Unscheduled medical visits	EMR	≤2/facility	
Validation				
Outcome Measure	Injurious falls	MDS and Chart Review	>90% sensitive, >95% specific	

the provider accepted one or more recommendations / number of patients with a medication recommendation; % of staff that indicated they were satisfied or very satisfied with the ILS; proportion of staff that attended one or more virtual case based education sessions

(Secondary) number of total medication recommendations accepted/ total number of medication recommendations; proportion of staff that attended two or more virtual cased based education sessions.

Demand: We will use the FRAiL model to identify residents at greatest risk of injurious falls who are eligible for the ILS Program. Residents with an estimated 2-year risk of hip fracture of ≥5%, or similar target, will be considered high risk and eligible for the program. The facility staff will also be able to refer other at risk patients for participation in the program. Other demand outcomes include the proportion of high risk residents with one or more deprescribing recommendations or with a recommendation for osteoporosis treatment, AND referral rates to virtual case based education sessions, defined as the proportion of high risk residents discussed in these sessions.

Fidelity: At each facility, we will identify targeted staff including nurses and medical providers (physicians, nurse practitioners, or physician assistants) who will be asked to complete the program checklists. Our primary measure of fidelity will be the proportion of staff that complete ≥ 75% of requested checklists. As a secondary fidelity measure we will examine the proportion of resident checklists completed by a provider.

Practicality: We will estimate cost by monitoring the amount of time the IP nurse spends on each eligible resident. Other outcomes include the estimated amount of time the staff spend on the ILS service by self-reported survey AND the six-month attrition of eligible residents from the NH facility due to transfer, discharge to community, or death, as determined by the IP nurse from chart review.

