- Validate Injurious Falls (Aim2c) - We will compare the occurrence of falls with injuries using MDS data with the occurrence according to chart review. The MDS defines major injury as any fall resulting in a fracture, joint dislocation or intracranial hemorrhage, whereas a minor injury includes falls resulting in abrasions, lacerations requiring sutures, hematoma, or pain. Participating facilities (Croasdaile Village and Hebrew Rehabilitation Center) will be asked to provide limited MDS data for all residents in the facility. A research assistant will conduct a chart review (all provider and nursing notes from EMR) of a random sample of approximately 300 patients to determine whether any injurious falls were documented. Agreement between the MDS and chart review will be compared using Cohen's Kappa test. We will also calculate the sensitivity, specificity, and positive and negative predictive value of the MDS to identify injurious falls, as compared with the gold standard of chart review.

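### Does the random draw of about 300 charts leave the Aim 2c estimate of MDS sensitivity on too few injurious falls, so that the sampling plan should change?

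*Combined protocol and SAP*

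**What the plan says.** Section 10 (Aim 2c) asks two facilities to "provide limited MDS data for all residents in the facility". A research assistant then reviews the charts "of a random sample of approximately 300 patients to determine whether any injurious falls were documented". MDS and chart are compared by kappa, sensitivity, specificity and predictive values, with the chart as reference. Table 1 in section 2.4 gives the goal for injurious falls as ">90% sensitive, >95% specific".

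The rates needed for an expected count are in section 2.2: "150 falls/100 bed years", and "Five to eleven percent of falls in the NH result in major injury", with major injury "defined as a fracture, joint dislocation, laceration requiring sutures, or serious hemorrhage". Section 10 uses the MDS definitions, under which "a minor injury includes falls resulting in abrasions, lacerations requiring sutures, hematoma, or pain". A sutured laceration is therefore major in the background and minor in the validation.

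Section 6.3 mentions MDS data and a falls log for the 6 months after implementation. Section 11.1 requests both for long-stay residents during the study, and section 2.5 gives each facility 18 months of participation. The Aim 2c text fixes no window. Section 10 describes the analysis as largely descriptive.

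**The concern.** Only residents whose chart shows an injurious fall contribute to sensitivity; the other charts inform specificity. If such falls are rare, 300 charts may contain very few of them, and a sensitivity reported without an interval could look as if it met the 90% goal when the true value was well below. Aim 2c exists to validate the outcome of a later pragmatic trial, so an over-optimistic figure would carry forward. The facilities also supply MDS codes for every resident and a falls log for long-stay residents, and neither is used to pick charts likely to hold an event. It seems that the same 300 charts could yield more information.

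**Working it through.** **The stated figure.** The plan gives no inputs for its 300 charts, so that number cannot be reproduced. The only precision statement in section 10 concerns medication adherence in 80 residents.

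**Expected cases.** Inputs are 300 charts (section 10), and 1.5 falls per bed-year with 5% to 11% causing major injury (section 2.2).

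- Falls = 300 × 1.5 × years × share.
- Residents with at least one = 300 × (1 − exp(−1.5 × years × share)), assuming Poisson counts.

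The documents give no share for any injury; 20% to 40% of falls is an assumption. Intervals are exact (Clopper-Pearson) 95%, for results just above 90%. Denominators are falls for major injury and residents for any injury.

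| Case definition | Window | Falls | Residents | Exact 95% CI |
|---|---|---|---|---|
| Major | 6 months | 11.25–24.75 | 11–24 | 10/11: 59–100%; 23/25: 74–99% |
| Major | 12 months | 22.5–49.5 | 22–46 | 20/22: 71–99%; 46/50: 81–98% |
| Major | 18 months | 33.75–74.25 | 32–66 | 31/34: 76–98%; 68/74: 83–97% |
| Any (assumed share) | 6 months | 45–90 | 42–78 | 38/42: 77–97%; 71/78: 82–96% |
| Any (assumed share) | 12 months | 90–180 | 78–135 | 71/78: 82–96%; 123/135: 85–95% |

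The MDS definition moves sutured lacerations out of the major group, so the major-injury counts are probably somewhat high. Since "Approximately one-half of injurious falls are fractures", fractures alone would be about half of them (6 to 12 in 6 months), but no goal is set for fractures.

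**What the smallest case can show.** With 25 of 25 detected, the lower limit is 86.3%; at least 36 cases with no misses are needed for it to exceed 90%. If true sensitivity were 80%, the observed value would still exceed 90% with probability 32% on 11 cases and 10% on 25. If it were 70%, the figures are 11% and 0.9%.

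**Specificity.** About 95% observed in 275 to 289 residents without an event gives roughly 92% to 97%, whatever is done about sensitivity.

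**The alternative draw.** Consider reviewing every MDS-coded or logged injury plus random samples of the rest, weighted back, with 300 charts in all. It was simulated for major injury over 6 months. The simulation assumed MDS sensitivity 0.90 and specificity 0.97, prevalence 0.037 or 0.079, and a log that flags 25% to 90% of the injuries the MDS misses. The reduction in root-mean-square error of sensitivity was:

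- 1–3% with 320 residents in the frame
- 1–15% with 400
- 6–29% with 600
- 7–38% with 800

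A repeat of the simulation put the best case at about 35%. If the log flags none of the missed injuries, the change runs from −2% to 7% across these frames. For specificity and kappa the reduction is 2–4% at 320 and 30–40% at 800.

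The frame size is not documented. Two homes at the 80-bed floor give 2 × 80 = 160 long-stay beds. Section 2.6 implies 80/0.20 = 400 long-stay residents in four homes, or 200 in an average pair. A random sample of about 300 from all residents implies more than 300, by an unknown margin.

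**Intervals under each design.** With the stratified draw, a percentile stratified bootstrap of nominal 95% covered the true sensitivity in only 62% to 92% of runs. When no missed case was drawn, in up to 38% of runs, it collapsed to 100–100%. Exact intervals under the planned random sample covered 98% to 99%.

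**The case for a change.** The best case for a change is that a numeric goal of 90% cannot be read without an interval. In every row of the table the lower limit for a result just above 90% stays below 90%, so the problem does not depend on the narrow reading. Section 10 itself quotes a 95% interval for the adherence target in a part of the plan where no testing is intended, so leaving one out for Aim 2c departs from its own practice. Stating the window and injury level and giving intervals would cost almost nothing.

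This stands as a remark on reporting. The window, the case definition and the interval should appear with the results, and the differing treatment of sutured lacerations means the MDS definition should be applied to both sources. But these are details an analyst has to settle to build the 2×2 table at all, and exact intervals can be computed from that table afterwards. None of them alters which charts are drawn or what is estimated. The part that would alter the plan, the stratified draw, rests on frame size and log accuracy that the documents do not give.

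**Conclusion.** No change to the plan follows. The arithmetic is right: major injury over 6 months gives about 11 to 25 falls and intervals as wide as 59–100% or 74–99%. But the Aim 2c text compares falls with injuries, describes both major and minor injury, and asks whether any injurious fall was charted. The small count therefore needs an injury level and a window that this text does not state. At 12 months and any injury, with an assumed 20% to 40% of falls injurious, there would be about 78 to 135 resident cases and intervals of 82–96% to 85–95%.

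The missing window, case definition and intervals are gaps that analysts fill sensibly in a descriptive pilot with no decision rule. The sampling choice is a fair trade-off. The random draw gives unweighted estimates of all five measures, free of verification bias, and supports valid exact intervals. Enrichment would reduce the error in sensitivity by between about nil and about 35%, on undocumented conditions, would need weighting, and needs an interval method that holds up with few or no missed cases. Its more dependable gain is in specificity, already estimated to within about 3 percentage points, and in kappa. The conclusion rests on the general fall rates in section 2.2 applying at the two validation sites, and on the simulation's assumed MDS and log accuracy.

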11. DATA SECURITIES

11.1. Data Transfer Agreement

We will request a Memorandum of Understanding between Hebrew SeniorLife and each of the four facilities allowing for the facilities to share limited MDS information and falls log for all long stay residents during the study. Other data collected will not require a data agreement: for example the facility level data comes from public data sources and resident data will be obtained from residents' medical charts, and a brief nurse interview.

11.2. Safety Measures

Data recorded on paper by NH staff for the support of the program management or data collection (e.g., lists of eligible staff/residents, fall logs) as well as audiorecorded interviews, will be maintained in the study staff in a locked case at all times when in the facility, and transported back to Hebrew SeniorLife and/or Duke University School of Medicine to be stored in a locked cabinet. PHI/data for eligible residents will be stored on secure Duke servers accessible only to study staff, and communicated to providers by secure email behind the Duke firewall.

All other data (e.g., EMR reports, chart abstraction) will be entered directly into a research database (REDCap) stored behind the Hebrew SeniorLife firewall. Only IRB-approved study staff will have access to these data. The co-PIs and informatics personnel bear primary responsibility for overseeing privacy and security of research data. Risk mitigation strategies include: 1) developing a limited dataset with direct identifiers maintained separately in a cross-walk file as soon as data collection is completed; 2) restricting access to folders containing research data to approved personnel only; 3) individual research data will be used only for analyses to complete study aims; 4) not transmitting individual data outside the HSL firewall; 5) never storing research data on a computer hard drive.

Should any incident such as theft or loss of data, unauthorized access of sensitive data or non-compliance with security controls occur it will be immediately reported according to HSL policy. All incidents regarding information security/privacy incidents will be reported to the HSL IRB and NIH within 24 hours of acknowledgement of issue. Reporting of results, such as in scientific papers and presentations, will never identify individual subjects. Data will be presented in aggregate and individual-level data will not be published.

11.3. Data Management

Data management and analysis for the study will take place at HSL under the direction of the informatics and biostatistics cores at the Marcus Institute for Aging Research (IFAR). Audio recorded interviews will be transcribed at Duke University with identifiers removed, whenever possible, and stored on Duke University's secure IT network. GMR Transcription Services, Inc. will be provided with the audio files, which are considered protected health information. Duke will establish a services contract with GMR Transcription Services for this project. All access to data is restricted to those on the research team who have been authorized by the PI to use this information. The HSL information technology (IT) department adheres to all the policies and practices under HIPAA regulations and is responsible for securing IFAR's IT infrastructure including physical servers and application software. IFAR has

established additional sensitive data policies and procedures in concert with the IRB to ensure safe data handling by faculty and staff.

12. PARTICIPANT RIGHTS AND CONFIDENTIALITY

12.1. Institutional Review Board (IRB) Review

This protocol and the HIPAA waiver applications will be reviewed and approved by Hebrew Senior Life's IRB. Duke University School of Medicine and Brown University will cede IRB review to Hebrew SeniorLife. Continuation of study is contingent on annual review and approval by the IRB. Any changes to study protocol or materials will be submitted to the IRB for review and approval prior to implementation.

12.2. Informed Consent

Because the ILS program poses minimal risk to subjects and represents best practices for medication optimization, we will request a waiver of individual authorization for disclosure of personal health information necessary to screen and follow residents. All long-term stay residents/families in the facilities will be mailed a letter describing the study with the option to opt out, as described above. Staff will provide verbal assent to provide feedback on study feasibility and acceptability, but no PHI will be recorded and a waiver of informed consent will also be requested for this minimal risk activity.

We are audiorecording and transcribing stories from a subset of residents, proxies, and staff about their fall prevention experiences. While transcripts will remove all names, the stories themselves may remain identifiable. Therefore, we will approach potential subjects for informed consent (non-written).

For the patient/proxy interviews, residents may lack capacity to consent for research due to cognitive impairment. Those with severe dementia indicated in their medical record will be unlikely to participate in the interview, and their proxy will be contacted as below. Those with moderate dementia indicated on their medical record will be approached in their room for assent to contact their proxy and participate in an interview together with their proxy; those who agree will have their proxy contacted as below. Those with no or mild dementia indicated on their medical record will be approached in their room and the study procedures described. We will then administer the Evaluation to Sign Consent (ESC) measure, which is an assessment of understanding that has been validated in NH residents (see attached ESC). Those who are able to describe a risk of participation and summarize study activities will be asked to proceed with the interviews (verbal informed consent). They will have as much time as they choose to consider and read the informed consent document. Phone numbers of study staff will be provided to answer additional questions. Those who do not pass the ESC will be asked for assent, and if provided their proxy contacted as below. Proxies will be contact in-person if encountered in the NH, or by phone if not. Study procedures will be described and written informed consent obtained as above. Proxies are assumed to have capacity to provide informed consent for research for this low risk study by virtue of their designated role as proxy for a vulnerable older adult. Phone numbers of study staff will be provided to answer additional questions.

12.3 Participant Confidentiality

This trial will be granted a HIPAA Waiver of Requirement for Authorization for Release of Protected Health Information for Research Purposes from the Hebrew Senior Life IRB. In order to preserve confidentiality, subjects will be assigned a study number for tracking and reporting purposes. All physical documentation and IT assets are stored in a locked areas within the participating NHs and within HSL, monitored 24-hours a day by security personnel, and

accessible only by authorized employees. Access to the HSL cooperate computer network is strictly prohibited and all electronic research data will be stored on dedicated IFAR systems located on our private network. Access to these data will be limited to study personnel on a "need to know" basis. If a NH resident is deemed ineligible for the study, all personal health information obtained for screening purposes will be destroyed as soon as possible.

Benzodiazepines	
 Used for insomnia, OR Used for other sleep disorder and alternative therapies not tried, OR Well-controlled mental health condition AND no acute anxiety for 1 year, OR Restless Legs Syndrome (RLS)/ Periodic Limb Movement Disorder (PLMD) 	
 25% dose reduction from starting dose every 2 weeks, 12.5% last 2 weeks (over a total of 8 weeks) If withdrawal symptoms appear (see "Monitoring"), maintain the current dose for one to two additional weeks and then resume the taper 	
 2 MDS assessments post intervention: MDS items pertaining to mood, behaviors and function (ADLs) Chart review at 1 and 4 months post intervention: behaviors, worsening psychiatric symptoms, insomnia, functional decline hospitalizations, ED visits 	
 Nursing to notify MD/NP for withdrawal symptoms during medication reduction period including insomnia, anxiety, irritability, and gastrointestinal symptoms (End date for this order is the same end date of the taper) 	
 For insomnia, employ non-pharmacologic strategies described below if insomnia reoccurs or persists during tapering If used for RLS/PLMS, may try dopamine agonist If anxiety recurs and drug therapy is required, consider a selective serotonin reuptake inhibitor (SSRI) antidepressant, particularly citalopram or sertraline
Antipsychotics	
 Used for behavior problems in or symptoms of dementia (e.g., psychosis, agitation, aggression) OR Well-controlled mental health condition AND no psychosis 	
 Dementia with behaviors: 25% dose reduction every 2 weeks with goal of discontinuing or lowest dose possible to control symptoms (over a total of 8 weeks) Other 	
 2 MDS assessments post intervention: MDS items pertaining to mood, behaviors and function (ADLs) Chart review at 1 and 4 months post intervention: behaviors, worsening psychiatric 	
 Nursing to notify MD/NP for dyskinésias, insomnia, nausea, worsening psychosis, aggression, or hallucinations during medication reduction period (End date for this order is the same end date of the taper) 	
 For insomnia, behavioral strategies, specifically consistent wake-sleep times, opening curtains during the day to maximize bright light exposure, increasing daytime activity, decreasing napping, and

	
 past year AND dose higher than minimal effective dose, OR Used for insomnia 	
 mental health condition: 25% dose reduction every 2 weeks with goal of minimal effective dose or lowest dose to control symptoms. Insomnia: 25% dose reduction every 2 weeks with goal of discontinuation 	
 symptoms, insomnia, functional decline hospitalizations, ED visits 		
 toileting before bed
Antidepressants	
 Well-controlled symptoms on stable dose >1 year 1st episode of depression OR dose > minimal effective dose No history of symptom relapse on discontinuation in the prior 2 years 	
 Recurrent: 50% dose reduction every 2 weeks to minimal effective dose or lowest dose to control symptoms (over a total of 8 weeks) 1st episode: 50% dose reduction every 2 weeks to d/c or lowest dose to control symptoms 	
 2 MDS assessments post intervention: MDS items pertaining to mood, behaviors and function (ADLs) Chart review at 1 and 4 months post intervention: behaviors, worsening psychiatric symptoms insomnia, functional decline hospitalizations, ED visits 	
 Nursing to notify MD/MP for withdrawal symptoms, including akathisia, anxiety, chills, gastrointestinal distress, headache, insomnia, irritability, malaise, myalgia, during medication reduction period (End date for this order is the same end date of the taper) 	
 If drug therapy is necessary, consider an SSRI, particularly citalopram or sertraline
Hypnotics	
 Periodic insomnia not impacting quality of life 	
 50% dose reduction every 2 weeks to d/c If withdrawal symptoms appear (see "Monitoring" 	
 2 MDS assessments post intervention: MDS items pertaining to mood, behaviors and function 	
 Nursing to notify MD/NP for withdrawal symptoms, including insomnia, anxiety, irritability, and gastrointestinal 	
 Melatonin Behavioral strategies, specifically consistent wake-sleep times, opening curtains during the day to

		
"), maintain the current dose for one to two additional weeks and then resume the taper
	
 (ADLs) Chart review at 1 and 4 months post intervention: behaviors, worsening psychiatric symptoms, insomnia, functional decline hospitalizations, ED visits 	
symptoms, during medication reduction period. (End date for this order is the same end date of the taper)
	
maximize bright light exposure, increasing daytime activity, decreasing napping, and toileting before bed

